2.2.2 Screening activities performed after a consent for screening has been signed

The following activities will be performed only after the subject has signed the study consent or the consent for study # 01C0129 (provided the procedures are permitted on that study) on which screening activities will be performed within 28 days prior to enrollment unless otherwise indicated.

Assessments performed at outside facilities or on another NIH protocol within the timeframes below may also be used to determine eligibility once a participant has signed the consent.

- Complete medical history and physical examination (including height, weight, vital signs, and ECOG performance status).
- Imaging for Phase I:
 - CT of chest, abdomen and pelvis or MRI, if clinically indicated.
 - A brain CT scan in participants with known CNS disease as described in Section **2.1.2.3**/ MRI scan if clinically indicated.
- Imaging for Phase II:
 - CT of the neck and chest⁺, or MRI, if clinically indicated, for participants with oropharyngeal cancer.
 - CT of skull, neck and chest⁺, or MRI, if clinically indicated, for participants with sinonasal SCC.

⁺Imaging of chest and neck ± skull is preferred but not required if a PET/CT is available from within the screening timeframe.

- For skin lesions, documentation by color photography, including a ruler to estimate the size of the lesion.
- EKG
- Clinical laboratory tests (within 16 days prior to enrollment):
 - Acute care panel (Na⁺, K⁺, Cl⁻, total CO₂, creatinine, glucose, blood urea nitrogen).
 - Hepatic panel (AST/GOT, ALT/GPT, total bilirubin, direct bilirubin).

- Mineral panel (albumin, calcium total, magnesium total, phosphorus).
- Urine or serum pregnancy test (β -HCG) for females of childbearing-potential and women < 12 months since the onset of menopause (within 5 days prior to enrollment).
- Hematology: complete blood count (CBC) with differential.
- Urinalysis.
- HBV, HCV, HIV testing including viral load for HCV, HBV and HIV if clinically indicated (within 3 months prior to enrollment). CD4 testing may also be required for HIV+ participants.
- Participants with a history of \geq grade 3 hypersensitivity reaction to monoclonal antibodies or M7824 will be evaluated by immunologist prior to enrollment.

2.3 PARTICIPANT REGISTRATION AND STATUS UPDATE PROCEDURES

Registration and status updates (e.g., when a participant is taken off protocol therapy and when a participant is taken off-study) will take place per CCR SOP ADCR-2, CCR Participant Registration & Status Updates found at:

<https://ccrod.cancer.gov/confluence/pages/viewpage.action?pageId=73203825>.

2.3.1 Screen Failure

Screen failures are defined as participants who consent to participate in the clinical trial but are not subsequently assigned to the study intervention or entered in the study. A minimal set of screen failure information is required to ensure transparent reporting of screen failure participants, to meet the Consolidated Standards of Reporting Trials (CONSORT) publishing requirements and to respond to queries from regulatory authorities. Minimal information includes demography, screen failure details, eligibility criteria, and any serious adverse event (SAE).

Individuals who do not meet the criteria for participation in this trial (screen failure) because of a transient lab abnormality may be rescreened.

2.3.2 Treatment Assignment Procedures

2.3.2.1 Cohorts

Number	Name	Description
1	Cohort 1	Subjects with advanced or metastatic HPV associated malignancies (Phase I)
2	Cohort 2	Subjects with newly diagnosed p16+ oropharyngeal cancer (Phase II): Arm 2A: Stage I (T1,T2 N1)/II/III Arm 2B: Stage II/III Note: Closed, Will Not Enroll
3	Cohort 3	Subjects with newly diagnosed stage II/III/IVA/IVB HPV+ sinonasal squamous cell cancer (Phase II)

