1.2.5 Clinical Experience with M7824 in HPV associated malignancies

The first in human dose escalation study of M7824 in patients with advanced solid tumors was conducted in the CCR (29). This work demonstrated on-target PD-L1 saturation and reduction of

circulating TGF β , early evidence of clinical efficacy including in a number of patients with HPV associated malignancies, and an acceptable safety profile. Continuation of this work in patients

[figure not shown]
Figure 2: Waterfall plot of confirmed best overall responses in patients with immune checkpoint inhibitor-naïve, recurrent/metastatic HPV-positive OPSCC (orange).

with metastatic HPV-associated cancers which was presented at AACR 2019 revealed a 35% response rate in 43 patients including a 43% response rate in 14 patients with p16+ OPSCC ([Figure 2](#)). These response rates are notably higher than the 12-24% response rate seen with blockade of PD-1 or PD-L1 alone for HPV-associated malignancies (e.g., cervical, anal, P16+ oropharyngeal) in the literature ([25, 30-35](#)). In addition, the median survival of the 43 enrolled patients with HPV-associated malignancies was 16.2 months and the median survival of the 36 enrolled patients with HPV positive malignancies was not reached after 16.8 months of follow-up. It should be noted that both of these median survivals are substantially longer than the median survival reported for similar populations receiving PD-1 or PD-L1 inhibitors alone (7.5-11.5 months) in the literature ([25, 32, 33, 35-37](#)).

Adverse events for M7824 were similar to those experienced with pembrolizumab or nivolumab, with the addition of the development of low-grade mucosal bleeding and keratoacanthomas (21%) known to be associated with systemic TGF β blockade. Treatment with M7824 induced the expansion of peripheral blood HPV 16 antigen-specific T cells to a greater degree in patients with a best overall response of CR, PR or SD compared to patients that had a best overall response of PD ([Figure 3](#)). These data suggested that M7824 could reverse suppression of HPV antigen-specific immunity in patients harboring HPV-positive malignancies refractory to standard treatments.

Figure 3: PBMC from patients treated with M7824 were assayed for HPV 16 antigen-specific cytokine production or CD107a positivity

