1.2.11 Rationale and background for performing immune assays

Multiple immune assays have been developed in the LTIB to better define the mechanism(s) involved in the use of specific novel agents, as monotherapy or in combination therapies, both for preclinical and clinical studies. In addition to analyses of biopsies, analyses of the peripheral immunome can provide valuable information where multiple samples can be analyzed over the course of a given therapy vs. pre-therapy. The LTIB has now developed and employed (45-48) a flow cytometry-based assay that can analyze 123 immune cell subsets in human PBMC from one vial of processed PBMC (approximately 10^7 cells). This assay will be used in this clinical trial to detect multiple (n=32) subsets of CD4+ T cells, CD8+ T cells (n=29), Tregs (n=7), B cells (n=5), NK (n=20), NKT (n=4), DC (n=10), and MDSC (n=16) to better understand the role of each agent. We also plan to evaluate changes in TCR clonal diversity both in biopsies and the periphery. One example of where these assays have been employed involves an ongoing first-in-human trial of the NHS-IL12 tumor-targeting immunocytokine (NCT01417546). TCR diversity increased 6-14-fold in biopsies of patients with a high or intermediate IFN- γ response but were unchanged or decreased with a low IFN- γ response. These findings also correlated with TIL in biopsies. We are also currently employing NanoString analyses to identify a gene signature in biopsies and PBMC, pre- and post-treatment.

The infiltration of p16-positive HNSCC with tumor infiltrating lymphocytes (TIL) tends to be greater than that observed in p16-negative HNSCC (49), possibly related to the presence of strong viral antigens. Supporting that these TIL are active and possess anti-tumor function, greater numbers of TIL present within p16-positive HNSCCs is positively correlated with increased survival after standard anti-cancer treatment and associated with an increased type I immune profile within the tumor (20). A meta-analysis of all published papers exploring TIL infiltration into p16-positive HNSCC demonstrated a strong, significant, positive correlation (50). Thus, changes in TIL infiltration into p16-positive HNSCCs after immunotherapy will be used for the primary outcome of the phase II portion of this study.

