2.3.2.2 Arms

Number	Name	Description
1	Arm 1A	HPV vaccine at 1×10^{11} Viral Particles (VP) (DL1) and at 5×10^{11} VP (DL2) Note: Closed, Enrollment Completed
2	Arm 1B	HPV vaccine at RP2D plus M7824 at 1200 mg
3	Arm 2A	HPV vaccine at RP2D given as neoadjuvant or induction therapy
4	Arm 2B	HPV vaccine at RP2D plus M7824 at 1200 mg given as neoadjuvant or induction therapy Note: Closed, Will Not Enroll

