2.3.2.3 Arm Assignment

Participants in Cohort 1 will be sequentially assigned to Arm 1A, to determine RP2D of PRGN-2009, and then Arm 1B, evaluating the combination of RP2D of PRGN plus M7824. Participants will be enrolled to these arms based upon a 3+3 dose escalation schema. In addition, Arm 1B will be expanded to a total of 10 evaluable participants to gauge the preliminary efficacy of the combination of PRGN-2009 and M7824 in participants with advanced disease.

Once the RP2D of HPV vaccine has been determined, p16+ oropharyngeal cancer participants in Cohort 2 and HPV-SNSCC participants in Cohort 3 will be assigned to Arm 2A (20 evaluable participants for Cohort 2, up to 2 for Cohort 3).

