10.4.9 Exploratory Analyses (Immune Responses)

Where feasible, exploratory immune analyses will be conducted to evaluate anti-tumor immune responses. Immune response will be assessed among all subjects treated in each cohort. The

magnitude of immune responses will be described. A subject will be considered evaluable for immune response if they receive at least one dose of treatment. The percentage of subjects with a positive immune response will be evaluated by cohort. For flow cytometry analyses on PBMC samples, Student T tests or Kruskal-Wallis and Wilcoxon rank sum tests as appropriate will be performed on percentages of TNF- α and/or IFN- γ expressing cells among the different cohorts to determine any significant differences in cell populations. For antigen specific T cell responses, a positive immune response is defined by CMI reactivity in *ex vivo* stimulation using a flow cytometric readout (cytokine production or CD107 expression). Antigen-specific peptide challenge assays require a readout of >250 reactive T-cells/million cells above the background (53).

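### Section 10.4.9 groups immune response by cohort, which on the protocol's only definition puts vaccine-alone and vaccine-plus-M7824 participants together; it should name arm and dose level (minor)

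*Combined protocol and SAP*

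**What the plan says.** Section 10.4.9 uses cohort as the grouping three times. The analysis set: "Immune response will be assessed among all subjects treated in each cohort". The summary: "The percentage of subjects with a positive immune response will be evaluated by cohort". The tests, on percentages of TNF-α and/or IFN-γ expressing cells: "among the different cohorts to determine any significant differences in cell populations".

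Section 2.3.2.1 is the only place where cohorts are defined, and the definition is by disease. Cohort 1 is "Subjects with advanced or metastatic HPV associated malignancies (Phase I"; Cohort 2 is newly diagnosed p16+ oropharyngeal cancer; Cohort 3 is newly diagnosed HPV+ sinonasal cancer.

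Treatment has a separate term, arm. In 2.3.2.2, Arm 1A is vaccine alone at two dose levels and Arm 1B is "HPV vaccine at RP2D plus M7824 at 1200 mg". Section 2.3.2.3 places both inside one cohort: "Participants in Cohort 1 will be sequentially assigned to Arm 1A, to determine RP2D of PRGN-2009, and then Arm 1B". Cohorts 2 and 3 receive vaccine alone (Arm 2A), since Arm 2B was closed before enrolment.

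No immune analysis by arm or dose level is written down anywhere.

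**The concern.** Section 1.2.11 gives the purpose of the blood-cell subset assay as "and MDSC (n=16) to better understand the role of each agent", and 1.1.3 looks for immune responses attributable to PRGN-2009 exposure. A rate that mixes vaccine-alone with combination participants serves neither aim.

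M7824 also acts on the signal being measured. Section 1.2.5 reports: "Treatment with M7824 induced the expansion of peripheral blood HPV 16 antigen-specific T cells". According to the Figure 3 caption, that was measured by cytokine production or CD107a. Section 10.4.9 defines a positive antigen-specific response by the same kind of readout.

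Two things are at stake. A single Cohort 1 figure would show neither a dose contrast nor the effect of adding M7824. And a test of Cohort 1 against Cohort 2 would compare a group in which most received M7824 with one in which nobody did, so an M7824 effect could be read as a difference between advanced and newly diagnosed disease.

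**Working it through.** The plan states no sample size or power for the immune analysis, so there is no figure to reproduce for this point. Its one powered calculation, the Phase II primary test in 10.2, does reproduce (success at 15 or more of 20: power 0.8042 against the stated 80.4%). It does not depend on the grouping, because it concerns one regimen in one cohort.

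**1. Who is in Cohort 1.** Table 8 (14.1.2) reports 3 on vaccine at 1×10^11, 3 at 5×10^11 and 11 on vaccine plus M7824. The total is 3 + 3 + 11 = 17, and the share given M7824 is 11/17 = 64.7%. These are the counts as reported there.

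**2. What a pooled rate shows.** Let V be the positive rate on vaccine alone (n = 6) and C the rate on the combination (n = 11).
- Pooled rate = (6V + 11C)/17.
- Pooled rate − V = (11/17)(C − V).

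Neither V nor C is given in the documents. Under assumed values:
- V = 30%, C = 80%: (1.8 + 8.8)/17 = 62%.
- V = 40%, C = 70%: (2.4 + 7.7)/17 = 59%.
- V = C: the pooled rate equals both, and pooling does no harm.

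**3. The pooled rate does not identify the M7824 effect.** Take a pooled result of 10/17 (59%, exact 95% CI 33–82%), again for illustration. It fits:
- 0/6 with 10/11 (two-sided Fisher p = 0.0006, combination higher);
- 3/6 with 7/11 (p = 0.64, no clear difference);
- 6/6 with 4/11 (p = 0.035, combination lower).

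**4. Cohort 1 against Cohort 2.** Suppose disease setting has no effect, so that Cohort 2 has rate V. The expected difference between the cohorts is still (11/17)(C − V). With V = 30% and C = 80% that is 0.647 × 50 = 32 percentage points, all due to M7824.

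**5. What a split can support.**
- Exact 95% CIs: 0/3 gives 0–71%; 3/3 gives 29–100%; 0/6 gives 0–46%; 10/11 gives 59–100%.
- Arm 1A DL1 against DL2, 3 versus 3: the smallest two-sided exact p, for Fisher or Wilcoxon, is 2/C(6,3) = 2/20 = 0.10. Significance at 0.05 is impossible.
- Arm 1A (n = 6) against Arm 1B (n = 11), two-sided Fisher power under assumed rates: 49% for 30% versus 80%, 68% for 20% versus 80%, 85% for 20% versus 90%.
- The sinonasal group has at most 2 participants (2.3.2.3).

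**The case against.** No sentence tells the analyst to pool the arms. Section 10.4.5 tabulates adverse events within dose cohorts, 10.4.8 describes a cohort displayed inside a larger group, and the précis calls the combination a third dose level. Someone used to dose-escalation trials could take cohort in 10.4.9 to mean dose group. The planned tests also sit oddly with the disease definition, under which one of three groups has at most 2 people. This stands: a reader might infer that the plan has decided to merge the regimens, and the documents do not establish that. They do establish that the term is used inconsistently and that the defined meaning merges the regimens. The by-dose reading is not complete either, since it does not say how Phase II participants, shown in Table 8 at the same 5×10^11 dose as DL2, are to be grouped.

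A reader might also infer that the role of each agent is lost. It is not: arm and dose level are assigned per participant, so the data can be split at any time. The fault lies in the specified summary.

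A third inference would be a fixed overstatement of the vaccine response rate. Assumed counts of 2/6 and 9/11 give 11/17 = 65% pooled against 33% on vaccine alone, a gap of 31 points. But those counts appear nowhere in the documents, and nothing says that the Cohort 1 figure will be presented as a vaccine-alone rate.

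Finally, the aim in 1.2.11 is stated for the subset-phenotyping panel, not for the antigen-specific rate in 10.4.9. That is correct, and the conflict with that rate is therefore one of purpose rather than of direct contradiction. The overlap of M7824 with the measured readout does not depend on it.

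**Conclusion.** The point holds as a minor one. On the protocol's own definition, 10.4.9 combines three regimens (3, 3 and 11 treated, 65% with M7824) in one immune-response summary, and it sets that group against vaccine-only cohorts. Because 10.4.5 uses the word differently, this is the literal reading but not the only one. Either way, the grouping is left open to choice after the results are seen.

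The group sizes are from Table 8; every response rate above is an assumption. The distortion is (11/17)(C − V): zero if the two rates are equal, about 32 points for an assumed gap of 50, and opposite in sign if the combination responds less often.

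The analysis is exploratory and done where feasible. The recommended dose, the DLT evaluation, the Phase II primary endpoint and all secondary endpoints are unaffected.

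**What to change.** In 10.4.9, replace the by-cohort grouping with grouping by arm and dose level: Arm 1A DL1, Arm 1A DL2, Arm 1B, Arm 2A oropharyngeal and Arm 2A sinonasal. Then add four limits:
- Report descriptively, with exact confidence intervals for the positive-response rate.
- Make no formal test of DL1 against DL2, and none involving the sinonasal group. Putting the new grouping into the existing test sentence without this limit would prescribe comparisons among groups of 3, 3 and at most 2.
- Treat any Phase I against Phase II contrast as descriptive. After the split it remains confounded by prior therapy (2.1.1.4) and by the different vaccine schedules (3.2.1).
- Do not report a rate that pools M7824-treated and vaccine-only participants as a vaccine response rate.

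The cost is a few lines of text in 10.4.9, with no new data or procedures. The downside is wide intervals in the small groups, for example 0–71% for 0/3.

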2.3.2.2 Arms

Number	Name	Description
1	Arm 1A	HPV vaccine at 1×10^{11} Viral Particles (VP) (DL1) and at 5×10^{11} VP (DL2) Note: Closed, Enrollment Completed
2	Arm 1B	HPV vaccine at RP2D plus M7824 at 1200 mg
3	Arm 2A	HPV vaccine at RP2D given as neoadjuvant or induction therapy
4	Arm 2B	HPV vaccine at RP2D plus M7824 at 1200 mg given as neoadjuvant or induction therapy Note: Closed, Will Not Enroll

2.3.2.3 Arm Assignment

Participants in Cohort 1 will be sequentially assigned to Arm 1A, to determine RP2D of PRGN-2009, and then Arm 1B, evaluating the combination of RP2D of PRGN plus M7824. Participants will be enrolled to these arms based upon a 3+3 dose escalation schema. In addition, Arm 1B will be expanded to a total of 10 evaluable participants to gauge the preliminary efficacy of the combination of PRGN-2009 and M7824 in participants with advanced disease.

Once the RP2D of HPV vaccine has been determined, p16+ oropharyngeal cancer participants in Cohort 2 and HPV-SNSCC participants in Cohort 3 will be assigned to Arm 2A (20 evaluable participants for Cohort 2, up to 2 for Cohort 3).

2.4 BASELINE EVALUATION

All subjects are required to complete baseline evaluations within two weeks (four weeks for Phase II imaging) prior to the first dose of the study drug (any screening evaluation done within this time period can also serve for the baseline evaluation unless otherwise indicated):

- Physical exam including weight, ECOG performance status and vital signs.
- Skin assessment.
- Medical history (Concomitant Medications and Baseline Signs and Symptoms evaluation).
- Imaging for Phase I*:
 - CT of chest, abdomen and pelvis or MRI, if clinically indicated.
 - A brain CT scan in participants with known CNS disease as described in Section [2.1.2.3](#)/ MRI scan if clinically indicated.
- Imaging for Phase II*:

- CT of the neck[†] and chest[‡], or MRI, if clinically indicated, for participants with oropharyngeal cancer.
- CT of skull[†], neck[†] and chest[‡], or MRI, if clinically indicated, for participants with sinonasal SCC.

^{*}Imaging for baseline should be within 2 weeks (for Phase I) or 4 weeks (for Phase II) prior to the first dose of study drug and is not required if available within the baseline timeframe. Imaging performed at outside facilities within the timeframe may also be used for baseline.

[†]Imaging of chest is not required if a PET/CT is available within the baseline timeframe.

[‡]The CT component of a PET/CT obtained within the baseline timeframe may be used as CT of the neck ± skull per PI discretion.

- Urine or serum pregnancy test (β -HCG) for females of childbearing-potential and women < 12 months since the onset of menopause (within 5 days prior to study therapy).
- Acute care panel (Na⁺, K⁺, Cl⁻, total CO₂, creatinine, glucose, blood urea nitrogen).
- Hepatic panel (AST/GOT, ALT/GPT, total bilirubin, direct bilirubin).
- Mineral panel (albumin, calcium total, magnesium total, phosphorus).
- Thyroid tests (TSH and reflex free T₃ & T₄), lipase, amylase, C-Reactive Protein (CRP).
- Hematology: CBC with differential.
- Coagulation panel: PT, INR, and PTT.
- HLA typing (any time prior to study treatment initiation - may be deferred if it has been previously performed at the NIH). (For Phase II only)
- Urinalysis.
- For correlative studies: Blood and tissue sample will be collected. Please refer to Section [5.1](#) for details regarding samples to be collected and refer to the [Study Calendar](#) for collection timepoints.
- Creatinine phosphokinase (CPK).

[figure not shown]
3 STUDY IMPLEMENTATION

3.1 STUDY DESIGN

Phase I: Recurrent/metastatic HPV associated cancer

- A 3+3 dose escalation design will be used which will evaluate PRGN-2009 (HPV vaccine) at two dose levels (1×10^{11} and 5×10^{11} VP) given as monotherapy followed by an evaluation of the RP2D dose of PRGN-2009 in combination with 1200 mg (RP2D) of M7824.
- Dose escalation will follow the rules as outlined:
 - After completion of enrollment on DL1 of Arm 1A, enrollment to DL2 of Arm 1A will proceed if 0 out of 3 or 1 out of 6 participants in DL1 of Arm 1A experience a DLT.
 - After completion of enrollment on DL2 of Arm 1A, enrollment to Arm 1B will proceed if 0 out of 3 or 1 out of 6 participants in DL2 of Arm 1A experience a DLT.
 - If 2 participants in a given dose level of Arm 1A or Arm 1B experience a DLT, accrual to that arm will be halted.
- There will be a 4-week DLT evaluation period for each dose level.
- There will be a 1-week delay between the first three participants treated on a given dose level.
- All other participants will be enrolled a minimum of six days apart on the phase I portion of the protocol except between the last participant in one dose level and the first participant in the next dose level in which case the DLT period of 4 weeks will be the minimum wait time.
- In addition, Arm 1B will be expanded to a total of 10 evaluable participants to gauge the preliminary efficacy of the combination of PRGN-2009 and M7824 in participants with advanced disease.

[figure not shown]
Schema for Phase I

Phase II: Newly diagnosed stage I (T1,T2 N1)/II/III HPV-positive oropharyngeal cancer and newly diagnosed stage II/III/IVA/IVB HPV-positive sinonasal squamous carcinoma:

- Evaluation of HPV vaccine alone (Arm 2A) as neoadjuvant or induction therapy in HPV-positive oropharyngeal cancer (20 participants), and HPV-SNSCC participants (2 participants).
- After completion of induction immunotherapy participants will be referred back to their home institution for definitive standard of care therapy. At outside institutions, standard of care treatment will be performed and chosen solely by outside providers. NCI investigators will have no role in treatments received at outside institutions.

Schema for Phase II

Although positive HPV testing will not be required for the phase I or II portion of the protocol prior to enrolling, HPV testing will be offered as an exploratory endpoint and participants testing negative for HPV after enrolling or whose HPV status cannot be confirmed may be replaced with other participants for the primary efficacy analysis. Participants testing negative for HPV after enrolling or whose HPV status cannot be confirmed may continue to receive treatment on study.

3.1.1 Dose Limiting Toxicity (for first 3-6 participants enrolled on Arms 1A and 1B; phase I part of the study):

Dose-limiting toxicity (DLT) will be defined as any one of the following adverse events, possibly attributable to study drugs, that occur within 28 days of the HPV vaccine monotherapy or 28 days of starting the HPV vaccine + M7824 combination therapy:

- Any Grade 3 or higher bleeding episode requiring blood transfusion(s).
- Any Grade 4 or higher adverse drug reactions (ADRs) as defined by CTCAE v5.0 and assessed as possibly related to any agent by the Investigator, except for laboratory values that are asymptomatic or resolve to Grade ≤ 1 or baseline grade within 7 days without medical intervention.
- Any Grade 3 ADRs possibly attributed to any agent except for any of the following:

- Grade 3 flu-like symptoms or fever, as well as associated symptoms of fatigue, headaches, nausea, emesis which can be controlled with conservative medical management.
- Tumor flare phenomenon defined as local pain, irritation, or rash localized at sites of known or suspected tumor.
- Grade 3 Hgb decrease (< 8.0 g/dL) that is clinically manageable with blood transfusions or erythroid growth factor use does not require treatment discontinuation.
- Grade 3 laboratory values that are asymptomatic or resolve to Grade ≤ 1 or baseline grade within 7 days without medical intervention.
- Keratoacanthoma and squamous cell carcinoma of the skin.
- Any endocrinopathy that can be medically managed with hormone replacement
- Any grade 3 adverse drug reaction which can be medically managed with minimal risk to the participants (e.g., placement of a pleural catheter for recurrent inflammatory pleural effusions) and resolves to at least grade one or baseline grade within 72 hours.

Where clinically appropriate subjects enrolled on Arm 1 will receive one year of treatment during which subjects will be followed with surveillance scans using CT/MRI (as appropriate) every 6-12 weeks. On a case by case basis treatment beyond a year is allowed per investigator discretion. Subjects with evidence of disease progression after completing a year of treatment will be allowed retreatment. Patients might be taken off treatment for disease progression prior to completing one year of treatment, but where clinically appropriate, treatment beyond radiographic progression is allowed if in the opinion of the investigator the subject is benefiting from treatment. Subjects will be taken off treatment if unacceptable toxicity occurs and is attributed to all therapeutic agents. If a single agent is tolerated that agent may be continued.

